This Phase II, clinical trial is a double-blind, placebo-controlled, parallel group study. Adult daily smokers motivated to quit smoking were be randomized to guanfacine (6mg day ER) or placebo Sex will be a stratification variable (50% female). Following eligibility screening and randomization, participants were titrated to steady state medication levels over a 3-week period. Participants completed an 8-week treatment period combining medication with brief behavioral support and were followed 6 months post-treatment to assess the durability of medication effects. The primary outcome measure was rates of prolonged smoking abstinence at the end of the 8-week treatment phase.

ELIGIBILTY

Minimum Age: 18 Years

Maximum Age: 65 Years

Sex: All

Gender Based:

Accepts Healthy Volunteers: Yes

Criteria:

Inclusion Criteria:

Age 18-65

Able to read, write and comprehend English

Smoker

Able to take oral medications and willing to adhere to a medication regimen

Provide evidence of a stable living residence in the last 2 months, have reasonable transportation to the study site, and have no plans to move within the next 3 months or unresolved legal problems

Exclusion Criteria:

Any significant current medical conditions that would contraindicate smoking

Current Diagnostic and Statistical Manual of Mental Disorders (DSM-IV) abuse or dependence of other substances, other than nicotine dependence or alcohol abuse

Positive test results at intake appointment on urine drug screen for illicit drugs

Past 30 days use of any psychoactive drugs including anxiolytics and antidepressants

Women who are pregnant or nursing

Suicidal, homicidal or evidence of current mental illness such as schizophrenia, bipolar disorder or major depression, or anxiety disorders

Meeting DSM-IV criteria for current attention deficit hyperactivity disorder (ADHD)

Individuals who are currently taking medications known to be effective for smoking cessation or are regular users of other tobacco products in the past 30 days

Only one member per household can participate in the study

Specific exclusions for administration of guanfacine not already specified include:

EKG evidence at baseline screening for any clinically significant conduction abnormalities or arrhythmias

Known intolerance for guanfacine or any alpha blocker

History of fainting, syncopal attacks

Heart failure or myocardial infarction

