Impaired liver (as indicated by aspartate aminotransferase (AST), alanine aminotransferase (ALT) >3x normal)

Renal function (as indicated by estimated creatinine clearance <60cc/min)

Treatment with any antihypertensive drug or any alpha-adrenergic blocker

Use of any central nervous system depressant (e.g., phenothiazines, barbiturates, benzodiazepines)

Use of strong cytochrome P450 3A4 (CYP3A4) inhibitors (e.g., ketoconazole) or inducers (e.g., rifampin), or consumption of grapefruit juice

Subjects may not have donated blood in the past 8 weeks or have been involved in other investigational studies that involve substantial blood draws or medications unknown to us

STATISTICIAL CONSIDERATIONS

PRIMARY HYPOTHESIS: Guanfacine vs placebo will increase rates of prolonged abstinence during weeks 3 to 8 of the 8-week treatment period. Logistic regression was used to evaluate medication effects on the abstinence outcome.

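### The primary logistic regression names only the medication effect although sex is a stratification variable; adding sex is almost free and recovers a little power if sex predicts abstinence (minor)

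*Combined protocol and SAP*

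**What the plan says.** The design section (Study Design and Methods) describes a two-arm, placebo-controlled, parallel-group trial. Directly after the statement about randomisation it adds: "Sex will be a stratification variable (50% female"). The placement suggests randomisation stratified by sex, but the 50% figure could also mean an enrolment quota.

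The primary hypothesis, under Statistical Considerations, is: "Guanfacine vs placebo will increase rates of prolonged abstinence during weeks 3 to 8 of the 8-week treatment period". The whole analysis description follows: "Logistic regression was used to evaluate medication effects on the abstinence outcome". No covariate is named there, and no other section says that sex enters the model or that it is left out.

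**The concern.** When a trial stratifies its randomisation by a factor, the usual practice is to carry that factor into the primary model. Stratifying balances the factor between arms, which makes the treatment comparison more precise. A model that ignores the factor computes its standard error as if that balance had not been imposed. If the factor is prognostic, the test is then somewhat conservative in large samples and loses power.

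Under an enrolment quota the arm-only test is not conservative. Adjusting for a prognostic baseline variable still gains power.

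A second, smaller matter is what the odds ratio means. In logistic regression the treatment odds ratio conditional on sex differs from the odds ratio averaged over the sexes whenever sex is prognostic. The plan does not say which it reports, and its hypothesis is about rates rather than odds.

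**Working it through.** **Inputs from the document.** Two parallel arms; a binary outcome (prolonged abstinence, weeks 3 to 8); 50% female; logistic regression for the medication effect. The document states no sample size, power, alpha, rates or sex effect, so there is no planned figure to reproduce.

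**Assumptions.** 1:1 allocation; two-sided alpha 0.05; within-sex treatment odds ratio (OR) 2.5; placebo abstinence 15% or 20% on average; 60, 100 or 150 per arm (500 per arm as a large-sample check); sex OR 1, 2 or 4 (also 6 for type I error); likelihood-ratio test. Placebo rates by sex were solved to give the assumed average:

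| Sex OR | Average 15% | Average 20% |
|---|---|---|
| 2 | 10.7% and 19.3% | 14.6% and 25.4% |
| 4 | 7.0% and 23.0% | 9.8% and 30.2% |

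**Step 1: power gain, stratified reading.** Simulated trials with equal numbers of each sex within each arm, 100,000 per setting. Gain in percentage points from adding sex (placebo 15% / 20%):

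| Per arm | Sex OR 1 | Sex OR 2 | Sex OR 4 |
|---|---|---|---|
| 60 | 0.2 or less | 0.9 / 1.1 | 2.9 / 3.4 |
| 100 | 0.2 or less | 0.6 / 0.6 | 2.6 / 2.6 |
| 150 | 0.2 or less | 0.5 / 0.3 | 1.6 / 1.5 |

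The Monte Carlo standard error is at most 0.07 points. A separate large-sample Wald calculation with other rates (10% vs 20%, 15% vs 30%, 20% vs 35%; 60 to 250 per arm) gave gains of 0.0 points at sex OR 1, 0.09 to 0.83 at OR 2 and 0.2 to 2.1 at OR 3.

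**Step 2: power gain, quota reading.** Here 50% are female overall and the split between arms is left to chance. Over 60 to 150 per arm the gain was 0.5 to 0.7 points at sex OR 2 and 2.3 to 3.4 at OR 4. At sex OR 1 it ran from -0.2 to +0.1; a repeat simulation put the loss at about 0.1 to 0.35 points at 60 to 100 per arm.

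**Step 3: type I error of the arm-only test.** Under exact balance by sex, the large-sample ratio of the true variance to the variance the arm-only model assumes is

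r = 1 - ((pF - pM)/2)² / [p(1 - p)], and the actual level is 2 × [1 - Φ(1.96/√r)].

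- Sex OR 2, 15%: (0.193 - 0.107)/2 = 0.043; r = 1 - 0.00185/0.1275 = 0.9855; level 4.83%.
- Sex OR 4, 15%: (0.230 - 0.070)/2 = 0.080; r = 1 - 0.0064/0.1275 = 0.950; level 4.43%.
- At 20% the levels are 4.79% (OR 2) and 4.26% (OR 4).

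Simulation at 500 per arm agrees within about 0.1 point. This is a large-sample result. At 60 per arm and sex OR 2 the arm-only test rejected in 5.7% / 5.2% of null trials, so it is not below 5% there. The excess is not caused by omitting sex: with no sex effect the figures are 5.7% / 5.5%. It comes from the likelihood-ratio test at that size; the Wald test gives 4.2% at 15%. The sex-adjusted test ran at 5.2 to 5.7% at 60 per arm and about 5.0 to 5.3% at 100 to 500. Under the quota reading at 500 per arm the arm-only test held 5.0 to 5.1% at every sex OR.

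**Step 4: which odds ratio.** With a within-sex OR of 2.5, placebo 15% and sex OR 2, the placebo odds by sex are 0.107/0.893 = 0.120 and 0.193/0.807 = 0.239. Multiplying by 2.5 gives rates on guanfacine of about 23.0% and 37.4%, averaging 30.2%. The sex-averaged OR is (0.302/0.698)/(0.15/0.85) ≈ 2.46 after carrying full precision. At 20% it is 2.45. At sex OR 4 the values are 2.35 and 2.31.

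**The case against.** The strongest objection is that the plan is silent rather than wrong. The sentence names the effect of interest, and a model with arm plus sex fits it equally well. That stands: the text does not prove that sex was left out. It only means that someone following it literally would fit arm alone.

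A second objection is that the gain is not better information but a higher rejection rate. Under the stratified reading this is largely right. With the adjusted test's critical value set to match the arm-only test's null rejection rate, the gain at 100 per arm, 20% and sex OR 4 fell from 2.73 to about 0.5 points. But the unadjusted test is running below its nominal level there, and recovering that lost level is exactly what adjustment does. Under the quota reading the objection fails: in the same setting power rose 3.4 points with type I error at 5.2% for both models.

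Third, nothing in the document says that sex predicts abstinence, every magnitude is assumed, and the unstated choice between Wald and likelihood-ratio tests moves type I error more than omitting sex does at OR 2. All true, and the reason this is a minor point. Nor is adjustment strictly without cost: if sex has no effect and was not balanced by design, it can lose up to about 0.35 points.

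Finally, the analysis sentence is in the past tense in a document dated October 2021. If the analysis is done, the primary model cannot now be changed cleanly.

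**Conclusion.** The point holds as a minor improvement. The design singles out sex, and the analysis as written does not use it. On the assumptions above, adding sex is worth about 1 point of power or less up to a sex OR of 2 and about 1.5 to 3.5 points at OR 4, under either reading of the stratification statement. If sex is not prognostic, essentially nothing is gained or lost. Omitting sex introduces no type I error inflation. The arm-only test is conservative only under stratified randomisation, and then only in larger samples or with a strong sex effect. The difference between the conditional and averaged odds ratios is small (2.5 against about 2.45 at sex OR 2) but should be labelled. Confidence is moderate, because the document supplies none of the quantities that set the size and does not settle whether sex was in the fitted model.

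**What to change.** State the model in full, for example: *The primary analysis is a logistic regression of prolonged abstinence (weeks 3 to 8) on randomised arm with sex as a covariate; the odds ratio is conditional on sex.* Keep the unadjusted model as supportive. Because the hypothesis concerns rates, the sex-averaged abstinence rate in each arm and their difference can be reported from the same model.

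Say whether allocation was stratified by sex or 50% female was an enrolment quota. Name the test (likelihood-ratio or Wald).

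If the analysis has already been run without sex, say so, leave the primary result as it is, and present the sex-adjusted model as supplementary, labelled as added afterwards.

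The cost is a few words of text and one degree of freedom, or one extra model fit if results are in hand. It needs no extra participants, data or procedures, since the design already uses sex.

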STUDY PROTOCOL INCLUDING STATISTICAL ANALYSIS PLAN

OFFICIAL TITLE: Guanfacine Clinical Trial for Smoking Cessation

BRIEF TITLE: Guanfacine Clinical Trial for Smoking Cessation ([name], PI)

CLINICALTRIALS.GOV ID: NCT02051309

PROTOCOL DATE: October 7, 2021

Identifying effective medications for the treatment of tobacco dependence remains a high priority as the vast majority of smokers fail to maintain long-term abstinence even with FDA approved pharmacotherapies. One promising, yet relatively unexplored avenue for medication development for smoking cessation are medications which target stress-reactivity. Several lines of evidence suggest that stress is a primary mediator of smoking maintenance and relapse. Preclinical research demonstrates that noradrenergic pathways are involved in stress-induced reinstatement to nicotine, as well as nicotine-related reinforcement and withdrawal, and that their manipulation may be of potential therapeutic benefit for smoking cessation.

Guanfacine is an alpha2a adrenergic receptor agonist known to attenuate stress-induced reinstatement to alcohol and other drugs of abuse in preclinical studies. Guanfacine rescues the prefrontal cortex from detrimental effects of stress and improves working memory, attention, and behavioral control. In a study evaluating 3mg/day guanfacine for smoking cessation, we demonstrated that guanfacine was well tolerated, attenuated the effects of stress on smoking, reduced smoking-related reinforcement, improved cognition, and significantly reduced smoking during a brief treatment phase.

STUDY OBJECTIVE

To conduct a Phase II clinical trial evaluating the efficacy of guanfacine for smoking cessation. Using a double-blind, placebo-controlled, parallel group design, we randomized adult daily smokers to guanfacine (6mg/day ER, or placebo) combined with brief behavioral support for an 8-week treatment period.

STUDY DESIGN AND METHODS

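### Does the primary logistic regression leave out randomised participants who have no observed abstinence outcome?

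*Combined protocol and SAP*

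**What the plan says.** The statistical considerations section holds one hypothesis and one method. The hypothesis is "Guanfacine vs placebo will increase rates of prolonged abstinence during weeks 3 to 8 of the 8-week treatment period". The method is "Logistic regression was used to evaluate medication effects on the abstinence outcome".

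The study design section gives the order of events: "Following eligibility screening and randomization, participants were titrated to steady state medication levels over a 3-week period". It goes on: "Participants completed an 8-week treatment period combining medication with brief behavioral support and were followed 6 months post-treatment". It describes the endpoint as follows: "The primary outcome measure was rates of prolonged smoking abstinence at the end of the 8-week treatment phase".

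Nowhere do the documents name an analysis population, give the denominator of the abstinence rates, or say how a participant with unknown smoking status is coded. Nor do they mention restricting the analysis to completers or to observed outcomes.

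**The concern.** A logistic regression cannot use a record whose outcome is blank, and by default software deletes it. Here titration comes after randomisation and the outcome window closes at week 8, so there is time for losses that depend on the assigned treatment. If those who leave are mostly smoking, deleting them raises the apparent quit rate most in the arm that loses most people. With heavier loss on guanfacine, an inert drug could look effective. The design section's remark that participants completed the treatment period can be read as a hint that only completers count. If all this were so, the primary comparison would lose the protection of randomisation, and a choice made after seeing the data could move the result.

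**Working it through.** **What the text fixes and what it leaves open.** The order of randomisation, titration and outcome window is stated. The set of participants entering the model is not. Deletion of dropouts is an inference from software behaviour. Once missing status is coded, the same sentence describes a regression on every randomised participant.

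**Inputs.** The plan has no figure to reproduce: it gives no sample size, alpha, abstinence rate or dropout rate. All values below are assumptions:

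- true abstinence *p* among all randomised, the same in both arms (no effect), 10% to 25%;
- dropout *d*, 20% to 40%;
- every dropout smoking;
- 100 per arm;
- two-sided 5% test, so a nominal 2.5% chance of a false benefit.

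**Formulas.** The complete-case rate in an arm is *p*/(1 − *d*), so the odds are *p*/(1 − *d* − *p*). With no effect, the complete-case odds ratio (guanfacine to placebo) is (1 − *d*P − *p*)/(1 − *d*G − *p*). For example, with *p* = 0.20, *d*G = 0.40 and *d*P = 0.20, the rates are 33.3% and 25.0% and the odds ratio is 0.60/0.40 = 1.50.

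The chance of a false benefit uses a pooled two-proportion z-test with the normal approximation. Worked case: *p* = 0.15, 40% against 20% dropout, 100 per arm.

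- Rates are 0.15/0.60 = 0.250 (60 observed) and 0.15/0.80 = 0.1875 (80 observed); the difference is 0.0625.
- Pooled rate: 30/140 = 0.2143.
- Null standard error: √[0.2143 × 0.7857 × (1/60 + 1/80)] = 0.0701.
- Unpooled standard error: √[0.250 × 0.750/60 + 0.1875 × 0.8125/80] = 0.0709.
- Chance of a false benefit: 1 − Φ[(1.96 × 0.0701 − 0.0625)/0.0709] = 14.6%.

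**Results under no effect**, ranges over *p* from 10% to 25%:

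| Dropout, guanfacine / placebo | Complete-case odds ratio | False benefit, 100 per arm |
|---|---|---|
| 20% / 20% | 1.00 | 2.5% |
| 30% / 20% | 1.17 to 1.22 | 5.1% to 8.4% |
| 40% / 20% | 1.40 to 1.57 | 10.7% to 24.7% |
| 20% / 30% | 0.82 to 0.86 | 0.6% to 1.2% |
| 20% / 40% | 0.64 to 0.71 | 0.1% to 0.4% |

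So a false benefit needs more loss on guanfacine. More loss on placebo pushes the estimate against the drug.

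**With a real effect**, assumed 25% against 15%, the odds ratio among all randomised is (0.25/0.75)/(0.15/0.85) = 1.89. Complete-case analysis gives (0.25/0.35)/(0.15/0.65) = 3.10 with 40%/20% dropout and (0.25/0.55)/(0.15/0.45) = 1.36 with 20%/40%.

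**Is counting missing as smoking free of bias?** Above it is, but only because all dropouts were assumed to smoke. Suppose instead that true abstinence is 20% in both arms, among those lost as well as those seen, with 40%/20% dropout. Counting missing as smoking gives 0.20 × 0.60 = 12% against 0.20 × 0.80 = 16%. The odds ratio is (0.12/0.88)/(0.16/0.84) = 0.72, although the truth is 1.00. Complete-case analysis would give 1.00 here. The rule is sensible for a prolonged-abstinence outcome, but it leans against the arm that loses more people.

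**The case for a change.** The strongest case for acting is that the plan's silence is real, and nothing suggests that text was blacked out there. Without a coding rule, applying the one sentence literally to incomplete data gives a complete-case analysis. The direction of bias depends on which arm loses more, so a rule chosen late leaves room for discretion. Writing one down would take a few sentences and one extra model.

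The silence stands, and so does the arithmetic. The step from silence to a stated complete-case analysis does not. The remark about completing treatment sits in a past-tense account of the design and describes how long treatment lasted. The same sentence says participants were followed for 6 months, and nobody would take that as a statement that none were lost. Leaving treatment is also not the same as having no outcome. Someone who stops during titration may still be assessed, or may already be known to have smoked inside the window. Nothing in the documents says that people who stop treatment are no longer assessed.

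Nor do the documents support the heavy, one-sided loss on guanfacine that a large false benefit requires. Their only tolerability statement is favourable. It concerns an earlier study at 3 mg/day, so it settles little about the 6 mg/day used here.

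**Conclusion.** No change follows. The plan states no wrong rule that a better one should replace. It leaves the analysis set and the coding of missing abstinence unwritten, and the obvious way to fill that gap is to analyse all randomised participants as assigned, with unconfirmed abstinence counted as not abstinent. That fits the sentence as it stands and suits an endpoint that requires abstinence across a window.

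A complete-case analysis, if one had been run, could matter. With no true effect and a 20-point excess loss on guanfacine, the odds ratio would be 1.40 to 1.57 and the chance of a false benefit 10.7% to 24.7% at 100 per arm. With the excess loss on placebo, the odds ratio would be 0.64 to 0.71. With equal loss there would be no bias. These figures rest wholly on assumed abstinence, dropout and sample size, and on every dropout smoking. They show why a reader should look at the denominators when results are reported. They do not show a fault in the plan.

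### The primary logistic regression names medication as its only effect; sex, the stratification factor, and any baseline smoking measure are left unspecified

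*Combined protocol and SAP*

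**What the plan says.** The Statistical Considerations section of the combined protocol and SAP has two sentences. The first is the hypothesis: "Guanfacine vs placebo will increase rates of prolonged abstinence during weeks 3 to 8 of the 8-week treatment period". The second is the method: "Logistic regression was used to evaluate medication effects on the abstinence outcome". No covariate is listed, and nothing says that the model is unadjusted.

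Study Design and Methods gives the stratification: "Sex will be a stratification variable (50% female". Sex does not reappear in the analysis text.

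The same section describes those randomised as "Adult daily smokers motivated to quit smoking" and places screening before treatment: "Following eligibility screening and randomization, participants were titrated to steady state medication levels over a 3-week period". The inclusion criterion on smoking is a single word, smoker. Cigarettes per day, carbon monoxide, cotinine and a dependence score are not mentioned anywhere. The documents also give no sample size, alpha, power or expected abstinence rates.

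**The concern.** Two things are missing from the model statement.

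- **Sex.** Where randomisation is stratified on a factor, the analysis normally carries that factor, so that it matches the way patients were allocated. This is the better documented half of the gap, because the plan itself names the factor.
- **Baseline smoking.** Heaviness of smoking before treatment is an obvious candidate predictor of whether a smoker abstains. If it does predict abstinence, a logistic model that includes it gives a more powerful test of medication from the same participants.

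What is at stake is a modest amount of power in the trial's single stated efficacy test, and the discipline of fixing the model in advance. A covariate set left open can be chosen after the results are seen.

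**Working it through.** There is no figure in the plan to reproduce. The check asks how much power a baseline smoking term could add.

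**Inputs, all assumed.** Abstinence 15% on placebo and 30% on guanfacine; 125 per arm; two-sided 5% Wald test; no dropout; one standard-normal baseline covariate with an odds ratio of 1.0 to 2.5 per SD. The marginal arm rates are held fixed as the covariate strength varies.

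**Without the covariate.**

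- Log odds ratio = ln[(0.30/0.70) / (0.15/0.85)] = ln 2.429 = 0.887.
- Standard error = √[1/(125 × 0.15 × 0.85) + 1/(125 × 0.30 × 0.70)] = √(0.0627 + 0.0381) = 0.318.
- z = 0.887 / 0.318 = 2.794.
- Power = Φ(2.794 − 1.96) = Φ(0.834) = 79.8%.

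**With the covariate.** For each covariate strength, the intercept and medication coefficient of the conditional model are solved so that the arm rates average to 15% and 30%. The standard error comes from the expected Fisher information for intercept, medication and covariate, integrated over the covariate by Gauss-Hermite quadrature. Power is again Φ(z − 1.96).

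| Covariate OR per SD | Conditional OR for medication | Standard error | z | Power | Gain (points) |
|---|---|---|---|---|---|
| 1.0 | 2.43 | 0.318 | 2.794 | 79.8% | 0 |
| 1.5 | 2.49 | 0.322 | 2.830 | 80.8% | 1.0 |
| 2.0 | 2.61 | 0.331 | 2.893 | 82.5% | 2.7 |
| 2.5 | 2.74 | 0.341 | 2.959 | 84.1% | 4.3 |

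The standard error rises with adjustment. Power still improves because the conditional log odds ratio rises faster. In sample-size terms the gain is the squared ratio of the z values: at 2.0 per SD, (2.893/2.794)² − 1 = 7.2% more participants; at 1.5 it is 2.6%, and at 2.5 it is 12.1%.

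**Other assumed rates**, with n set for about 80% power by the two-proportion formula:

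| Rates | n per arm | Unadjusted | OR 1.5 | OR 2.0 | OR 2.5 |
|---|---|---|---|---|---|
| 10% vs 20% | 199 | 78.4% | 79.2% | 80.7% | 82.2% |
| 20% vs 35% | 138 | 78.9% | 80.0% | 81.9% | 83.8% |

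**Cross-check by simulation** (4,000 trials per cell, 15% vs 30%, 125 per arm). Unadjusted and adjusted power were 82.1% and 83.1% at 1.5 per SD, 82.0% and 84.6% at 2.0, and 80.5% and 85.8% at 2.5. With the arm rates fixed, unadjusted power cannot depend on the covariate, so the spread in its column is simulation noise. Exact binomial calculation puts it at 81.7%. The 5.3-point difference at 2.5 per SD therefore partly reflects a low draw in the unadjusted column, and the 4.3 points from expected information is the better figure. With a covariate of no prognostic value, the simulated loss was at most 0.5 of a point (60.2% to 59.7% at 75 per arm).

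The value of the sex term was not quantified. The case for it rests on matching the stratified randomisation.

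**The case against.** The strongest reply is that the plan is silent, not wrong. A reader might infer that the model was chosen to contain medication alone. The sentence does not say so, and a covariate set that is unspecified differs from one that is excluded. That stands, and the point is worded accordingly.

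A reader might also infer that enrolling daily smokers proves that a baseline smoking quantity was on file and was left unused at no saving. Daily status does have to be established before randomisation, but it is a yes/no fact, the same for everyone enrolled, and cannot serve as a covariate. The amount smoked may well have been recorded; the documents do not say so. The baseline smoking term must therefore be conditional on its having been collected. That baseline smoking predicts abstinence is likewise an assumption, with no figure for it in the documents.

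A third tempting inference is that omitting a prognostic covariate biases the estimate, because the odds ratio moves towards 1 and chance imbalance goes uncorrected. This does not hold. The unadjusted odds ratio is a valid marginal effect; it differs from the conditional one because odds ratios are non-collapsible. Under randomisation, chance imbalance is already allowed for in the standard error and does not invalidate the test.

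Last, the document is dated October 2021 and describes the analysis in the past tense. If the data are unblinded, adding a term is no longer a wording change. That also stands and shapes the remedy.

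**Conclusion.** The point holds as a gap in specification with a small, assumption-based cost in power. The primary model names neither the stratification factor nor any baseline smoking measure. At 15% vs 30% and 125 per arm, a baseline smoking term is worth about 1 to 4 points of power for covariate odds ratios of 1.5 to 2.5 per SD, and nothing if it is not prognostic. Every input to that range is assumed. The unadjusted test is valid, so adjustment is a gain in efficiency and not a repair of bias. It is a minor, desirable improvement. The sex term has firm support in the plan's own design; the smoking term depends on a measurement that the documents do not describe.

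**What to change.** State the primary model as logistic regression of prolonged abstinence on medication and sex. Add baseline cigarettes per day as a continuous term if that quantity was recorded at screening; if it was not, say so. State that the resulting odds ratio is conditional on these terms, and report the unadjusted result as a sensitivity analysis.

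The documents do not say whether treatment codes have been opened. If they have, keep the planned result as primary and label the adjusted model post hoc.

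The cost before unblinding is SAP wording and one or two model terms. The drawbacks are small. The reported odds ratio becomes conditional instead of marginal (for example 2.61 against 2.43 at 2.0 per SD), and the baseline smoking field must be complete for everyone analysed.
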